### **9.1.3. Severity of Adverse Event**

A summary of TEAEs by severity will be presented in a table. The severity that will be presented represents the most extreme severity captured on the eCRF page. The possible severities are measured on the CTCAE scale which goes from 1 to 5 where 1=‘mild’, 2=‘moderate’, 3=‘severe’, 4=‘life-threatening’ and 5=‘fatal’.

The severity of the AEs will be summarized by SOC, preferred term, study part, dose cohort, and overall. SOC and preferred terms within SOC will be presented by descending frequency based on overall count. If a participant reports more than one AE within the same preferred term, the AE with the maximum severity will be presented. If a participant reports more than one AE within the same SOC, then the participant will be counted only once with the maximum severity at the SOC level. If severity is missing, then Grade 3 “Severe” is assumed.

#### 9.1.4. Dose Limiting Toxicities

All DLTs will be summarized by SOC, preferred term, study part, dose cohort, and overall. DLTs will be presented using CTCAE grades, AEs that are not graded using the CTCAE scale are still recorded in the eCRF using the same mapping (1=‘mild’, 2=‘moderate’, 3=‘severe’, 4=‘life-threatening’ and 5=‘fatal’).

DLTs definitions by protocol regions are as presented in [Table 9-1](#).

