14.2.3 Severity

The medical assessment of severity will be determined by using the definitions specified in [Table 5](#).

Table 5: Adverse Event Severity

Category	Definition
Mild	The AE does not interfere with the participant's daily routine and does not require intervention; it causes slight discomfort
Moderate	The AE interferes with some aspects of the participant's routine, or requires intervention, but is not damaging to health; it causes moderate discomfort
Severe	The AE results in alteration, discomfort or disability which is clearly damaging to health

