**Table 9-1 DLTs Definition by Protocol Versions**

Global (ex-US/ex-Brazil), Brazil only	US only
DLTs are defined as any severe AE at least possibly related to FLT201 except for increases in ALT or AST that are not associated with increases in bilirubin.	DLTs are defined as any Grade 3 or greater AE that is deemed by the DMC to be possibly, probably, or definitely related to FLT201. Toxicities will be graded according to the National Cancer Institute (NCI) Common Terminology Criteria for Adverse Events (CTCAE) version 5.0.

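### SAP 9.1.4 pools DLTs judged under two definitions in one table, and SAP 9.1.3 describes two severity scales as if they were one

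*SAP*

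**What the plan says.** SAP Table 9-1 gives the DLT definition by protocol version.

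- Global (ex-US/ex-Brazil) and Brazil: "any severe AE at least possibly related to FLT201 except for increases in ALT or AST that are not associated with increases in bilirubin".
- US only: "any Grade 3 or greater AE that is deemed by the DMC to be possibly, probably, or definitely related to FLT201". The grading rule follows: "Toxicities will be graded according to the National Cancer Institute (NCI) Common Terminology Criteria for Adverse Events (CTCAE) version 5.0".

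SAP 9.1.4 puts both into one summary: "All DLTs will be summarized by SOC, preferred term, study part, dose cohort, and overall". There is no breakdown by definition or protocol version. Region appears only among the demographic characteristics (SAP 6.1), and country only in an enrolment breakdown (SAP 5.1.1).

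On severity, SAP 9.1.3 says of all TEAEs: "The possible severities are measured on the CTCAE scale which goes from 1 to 5". Protocol 14.2.3, Table 5, has three levels (mild, moderate, severe), and its top level reads: "The AE results in alteration, discomfort or disability which is clearly damaging to health". SAP 9.1.4 acknowledges that some AEs are not CTCAE-graded and assigns them a number by label, so that severe becomes 3. SAP section 14, on changes to the planned analysis, mentions neither the pooling nor the scale conversion.

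**The concern.** DLTs are named in the primary safety variable (SAP Table 2-1). The two definitions part company on transaminase rises, which protocol 13.2 describes as anticipated with this class of product and which head the AESI list in protocol 14.2.9. With two or three participants per planned cohort, one event classified differently changes a cohort's DLT proportion by a third or a half. A reader comparing cohorts in the pooled table cannot tell whether a difference reflects dose or the protocol version under which participants were assessed. The severity table has a related fault: a number from 1 to 5 does not carry the same meaning for every participant.

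**Working it through.** The plan states no figure for this point. The sample size rests on feasibility, so there is no power or alpha to reproduce. The check sets the definitions side by side, follows events through them, and adds simple arithmetic.

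**1. Definitions compared (SAP Table 9-1; protocol 14.2.3 and 14.2.4)**

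| Element | Global and Brazil | US |
|---|---|---|
| Severity threshold | rated severe | CTCAE v5.0 Grade 3 or more |
| Who judges relatedness | investigator, under the supplied protocol | DMC |
| ALT/AST rise without bilirubin rise | excluded | not excluded |

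The threshold in the first column is the Table 5 scale in the supplied protocol. The Brazil protocol's scale is not available.

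**2. Following events through**

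- Isolated Grade 3+ ALT/AST rise, judged related: a DLT in the US. Elsewhere it is excluded at any severity. The direction is certain.
- Any other related event: Table 5 *severe* and CTCAE Grade 3 rest on different criteria, and relatedness is assessed by different parties. The event may qualify under either definition and not the other, so the direction is unknown.
- Where the mixing occurs: SAP 3.1 says Part 2 is not run in the US. Mixing is therefore confined to Part 1 and the overall column.

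**3. Size for identical events (illustration)**

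Proportion = US participants with the event / participants in the group. Each event is an isolated Grade 3+ ALT/AST rise, and each one in a US participant is judged related by the DMC.

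- Cohort of 3, one event: 1/3 = 33% if that participant is in the US, 0/3 = 0% if not.
- Cohort of 3, one event in each participant: 0/3, 1/3, 2/3 or 3/3 (0%, 33%, 67%, 100%) with 0, 1, 2 or 3 US participants.
- Part 1 with 12 participants and three events: from 0/12 = 0% to 3/12 = 25%.

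**4. Size under assumed rates**

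The documents give no event rates, so these are assumptions. Let p be the chance of a DLT that both definitions would count, and q the chance of an isolated transaminase event that only the US definition counts, taken as independent.

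Global rate = p. US rate = 1 − (1 − p)(1 − q). For a rate r, the chance of at least 2 DLTs in 3 = 3r²(1 − r) + r³.

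| p | q | Global rate | US rate | At least 2 of 3, Global | At least 2 of 3, US |
|---|---|---|---|---|---|
| 5% | 5% | 5% | 9.8% | 0.7% | 2.7% |
| 5% | 30% | 5% | 33.5% | 0.7% | 26.1% |
| 10% | 5% | 10% | 14.5% | 2.8% | 5.7% |
| 10% | 30% | 10% | 37.0% | 2.8% | 30.9% |

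Example, p = 10% and q = 30%: 1 − 0.90 × 0.70 = 0.37, and 3 × 0.37² × 0.63 + 0.37³ = 0.309. At low q the definitions differ modestly. At q near 30% the definition alone moves the rate from well below the 33% that protocol 13.3.1.1 expects to about that level or above it.

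**5. Severity scale**

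Table 5 grades by effect on daily routine, need for intervention and damage to health, and has no life-threatening or fatal level. An event that needs intervention without harming health is moderate there. SAP 9.1.3 describes a five-level CTCAE scale for all TEAEs. Matching by label joins the words, not the criteria.

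**The case against.** The SAP discloses both definitions. Its DLT table has preferred-term rows, so a transaminase DLT would be visible. All AEs are listed, ALT, AST and total bilirubin are plotted by participant, and AESIs are tabulated separately. With about 18 participants, much can be reconstructed. TEAE incidence, the core of the primary variable, does not depend on DLT status or grade, and the severity table is only supportive. All analysis is descriptive. Escalation is reviewed by the DMC during the study, the 33% is an expectation and not an acceptance limit, and the dose–DLT model in protocol 15.3 is optional and absent from the SAP.

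Most of this stands and limits the rating. It does not repair the pooled count. A reader can set aside a transaminase row, but cannot see from that row whether bilirubin also rose, and cannot add back isolated rises in non-US participants, because those never enter the table. Setting the row aside also leaves the differences in grading and in who assesses relatedness.

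Three stronger readings are tempting and not supported.

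- That any given event counts in the US and not elsewhere. This is certain only for isolated Grade 3+ ALT/AST rises judged related.
- That observed cohort differences will be region differences, or that escalation decisions are compromised. The number and cohort of US participants are not given, and no rule uses the final table.
- That both definitions could simply be applied to everyone. Nothing shows that DMC relatedness, or CTCAE grades for non-laboratory AEs, exist for non-US participants.

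**Conclusion.** The point holds within limits: followed exactly, the SAP yields a DLT count by cohort and overall that has no single meaning. The affected area is Part 1 and the overall column. For one isolated, related Grade 3+ transaminase rise in a cohort of three the difference is 1/3 against 0/3. This assumes that US and non-US participants are both enrolled in Part 1, that such an event occurs, and that for a US participant the DMC judges it related. The SAP's description of severity is also inconsistent with protocol Table 5. The US and Brazil protocols and the eCRF were not available, so how severity was captured under each cannot be settled here. The documents do not say which DLT definition governs the pooled table; the passages must be reconciled. Rating: SHOULD-FIX.

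**What to change.** 1. In SAP 9.1.4, present DLTs by protocol version or definition beside the pooled column, for each cohort and overall.
2. Add one harmonised table for all participants, built from investigator relatedness, recorded severity, and ALT, AST and bilirubin results. Show the count with and without isolated ALT/AST rises. Derive laboratory grades from measured values by CTCAE v5.0, and flag DMC relatedness where it exists. Label the table as an approximation, not as the US definition applied to everyone. State whether the SAP's defaults for missing relatedness (9.1.2) and missing severity (9.1.3) apply.
3. Correct SAP 9.1.3 to state which severity scale was used under which protocol, and show severity by scale.
4. Record the pooling and the scale conversion in SAP section 14.

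The cost is SAP wording, additional columns, one further DLT table and the programming of laboratory grades. The downside is that more than one DLT count is reported, and that the harmonised count only approximates the US definition. The change does not choose between the two definitions and alters no clinical rule.

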**Table 9-1 DLTs Definition by Protocol Versions**

Global (ex-US/ex-Brazil), Brazil only	US only
DLTs are defined as any severe AE at least possibly related to FLT201 except for increases in ALT or AST that are not associated with increases in bilirubin.	DLTs are defined as any Grade 3 or greater AE that is deemed by the DMC to be possibly, probably, or definitely related to FLT201. Toxicities will be graded according to the National Cancer Institute (NCI) Common Terminology Criteria for Adverse Events (CTCAE) version 5.0.

#### **9.1.5. Serious Adverse Events**

SAEs are defined in the protocol. SAEs will be summarized by SOC, preferred term, study part, dose cohort, and overall.

Important medical events as described in the protocol that may jeopardize the participant or may require an intervention to prevent one of the above characteristics/consequences may be considered SAEs when, based upon medical judgment.

SAE data will also be presented in a listing.

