15.3 Analysis of Primary Safety Endpoints

Dose-limiting Toxicities

All DLTs will be summarised by cohort/dose level.

Although the dose escalation is based on an algorithm, the final data may be used, for example, to model the DLTs as a function of dose, adjusted for any potential confounders, to further refine any estimate of the MTD (e.g., to determine the probability of toxicity closest to a given threshold toxicity at some observed dose level). The uncertainty around the estimate of the true DLT rate may be provided in terms of 95% confidence intervals or 95% credible intervals.

Adverse Events

Frequency of treatment-emergent AEs and SAEs will be calculated for each body system and preferred term, and by dose level, for number of events and number of participants reporting the event. The severity of the AEs and the relationship to study medication will be summarised for each body system and preferred term by cohort/dose level.

Other Safety Endpoints

Safety endpoints including the following will be summarized descriptively by cohort/dose level.

- Change from baseline in laboratory data
- Change from baseline in 12-lead ECG data
- Change from baseline in physical examination data
- Change from baseline in vital signs data.

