**Table 2-1 Primary Objective and Endpoints - Safety**

Primary Objective	Primary Endpoints
To assess the safety and tolerability of a single IV administration of FLT201 in adults with Gaucher disease type 1 (previously treated and previously untreated).	
Primary safety variable: incidence of TEAEs (including DLTs) from Day 1 to the last follow-up visit.
 
Other safety endpoints: incidence of AEs, SAEs, and changes from baseline in vital signs, 12-lead ECG, physical examination, and laboratory assessments from Day 1 to the last follow-up visit.

Abbreviations: AE=adverse event; DLT=dose-limiting toxicity; ECG=electrocardiogram; IV=intravenous; SAE=serious adverse event; TEAE=treatment emergent adverse event.
	

Table 2-2 presents the secondary objectives and endpoints.

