##### **9.1. Adverse Events**

Any AEs that occur from the time the initial Informed Consent Form (ICF) is signed by a participant until the end of study visit. This includes events occurring during the screening phase of the study and regardless of whether FLT201 is administered.

For a full definition of AEs for this study, see the protocol.

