### **9.1.2. Relationship of Adverse Events to Investigational Medicinal Product**

The investigator will determine whether there is a reasonable causal relationship between the occurrence of the AE and exposure to IMP (FLT201) and non-investigational medicinal products (NIMP) (prednisolone/prednisone, methylprednisolone, and tacrolimus). If there is no valid reason for suggesting a relationship, then the AE should be classified as “Not Related.” Otherwise, if there is any valid reason for suspecting a possible cause-and-effect relationship between the IMP/NIMP and the occurrence of the AE, then the AE should be considered “Related.”

If the relationship to IMP/NIMP information is missing, then the corresponding AE is assumed to be related with reasonable possibility to the IMP/NIMP. If a participant experiences more than one occurrence of the same AE, the occurrence with the most-related relationship to IMP/NIMP will be used in summary tables.

The relationship of AEs to IMP/NIMP will be summarized by SOC, PT, study part, dose cohort, and overall.

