#### **9.1.7. Adverse Events of Special Interest (AESI)**

AESIs are defined in the protocol. AESIs will be summarized by SOC, preferred term, study part, dose cohort, and overall.

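### The SAP's SOC/preferred-term tables for SAEs, AESIs and relationship have no Day 1 or treatment-emergent limit, so as written they would include pre-infusion events of participants who are later dosed

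*SAP*

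**What the plan says.** **Endpoint window.** SAP Table 2-1 gives the primary variable as "incidence of TEAEs (including DLTs) from Day 1 to the last follow-up visit". The other safety endpoints cover "AEs, SAEs, and changes from baseline in vital signs, 12-lead ECG, physical examination, and laboratory assessments from Day 1 to the last follow-up visit", the first two as incidences. Protocol Table 3 sets the same Day 1 start.

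**Collection window.** SAP 9.1 takes AEs from signature of the consent form to the end-of-study visit and adds: "This includes events occurring during the screening phase of the study and regardless of whether FLT201 is administered". Protocol 14.2.1 and 14.3.2 collect AEs and SAEs over the same span.

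**Tables with no onset limit.**
- SAP 9.1.5: "SAEs will be summarized by SOC, preferred term, study part, dose cohort, and overall".
- SAP 9.1.7: "AESIs will be summarized by SOC, preferred term, study part, dose cohort, and overall".
- SAP 9.1.2 tabulates the relationship of AEs (not TEAEs) to IMP and NIMP, with this rule: "If the relationship to IMP/NIMP information is missing, then the corresponding AE is assumed to be related with reasonable possibility to the IMP/NIMP".

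**Tables that are limited.** SAP 9.1.6 restricts the non-serious table to treatment-emergent events. SAP 9.1.3 opens as a summary of TEAEs by severity, although its second paragraph goes back to AEs. The serious and IMP-related rows of the 9.1.1 overview are TEAE rows.

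**Protocol analysis text.** Protocol 15.3 says: "Frequency of treatment-emergent AEs and SAEs will be calculated for each body system and preferred term". SAP section 14 declares no change to the Day 1 window.

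**The concern.** The endpoint starts at infusion, but the event pool behind three detailed tables starts at consent, up to 16 weeks earlier. Nothing in 9.1.2, 9.1.5 or 9.1.7 tells a programmer to drop events with onset before infusion. An event that FLT201 cannot have caused would then stand under a dose cohort.

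Safety is the primary objective of this first-in-human dose-escalation study, and cohorts are very small. One misplaced event is visible in a by-dose percentage. The SAE table could also show more participants than the serious TEAE row of the overview, with nothing to explain the gap. Non-serious and serious events would be tabulated over different windows.

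The missing-causality rule makes a further error possible. It has no onset condition, so a screening AE whose causality field is blank becomes FLT201-related although it came before the dose.

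**Working it through.** **1. Which window each table uses**

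| Place in SAP | Term used | Limited to Day 1 or TEAE? |
|---|---|---|
| Table 2-1, AE and SAE incidence | AEs, SAEs | Yes, Day 1 |
| 9.1.1 overview, serious and IMP-related rows | TEAE | Yes |
| 9.1.3 severity, opening | TEAEs | Yes |
| 9.1.6 non-serious | treatment-emergent | Yes |
| 9.1.2 relationship | AEs | No |
| 9.1.5 serious | SAEs | No |
| 9.1.7 special interest | AESIs | No |

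The overview has separate rows for any AE and any TEAE, so the SAP treats the two terms as different.

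**2. Who can contribute.** SAP 4.4.2 makes the Safety Set (all who received any dose) the default for summaries. Screen failures therefore cannot enter. Participants who are dosed after an event in screening can.

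**3. Whether such events can occur.** Protocol Tables 1 and 2 record AEs at both screening visits, on Day -1 and pre-dose. Of the AESIs in protocol 14.2.9, a positive SARS-CoV-2 test, a raised hs troponin-T and a clinically significant ECG change can all precede infusion. Table 2 schedules the SARS-CoV-2 test within 72 hours before dosing, and troponin and ECG are assessed at screening and on Day -1.

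**4. Share of the counted window before infusion.** The protocol synopsis gives screening of up to 16 weeks and follow-up of 38 weeks with a 2-week window. The sum 16 + 38 + 2 = 56 reproduces its stated maximum duration. SAP 7.2.2 puts the end of study at Month 24 for US participants. I take this as 104 weeks and assume the same screening limit, since the US protocol is not among the documents.

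Share = screening / (screening + follow-up):
- 16 weeks' screening, 38 weeks' follow-up: 16/54 = 29.6%
- 16 weeks, 40 weeks: 16/56 = 28.6%
- 8 weeks, 38 weeks: 8/46 = 17.4%
- 4 weeks, 38 weeks: 4/42 = 9.5%
- 16 weeks, 104 weeks: 16/120 = 13.3%

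**5. Weight of one event.** If the participant has no post-infusion event in the same row, one pre-infusion event adds 100/n percentage points: 100 for n = 1, 50 for n = 2, 33.3 for n = 3, 8.3 for n = 12 and 5.6 for n = 18. Cohorts are planned at 2 or 3. Protocol 13.3.1.2 allows 1 when GCase activity is low and no DLT is seen.

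**6. Chance that it arises (assumption only).** The documents give no background rate. If each dosed participant had a 2%, 5% or 10% chance of a screening SAE or AESI, the chance of at least one among n is 1 - (1 - p)^n. That is 0.215, 0.460 and 0.718 for n = 12, and 0.305, 0.603 and 0.850 for n = 18.

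**The case against.** The strongest reply is that this is a missing qualifier, not a rule to include screening events. SAP section 9 bases the safety profile on TEAEs in a sentence that can be read as making SAEs part of them. Table 2-1 fixes the window at Day 1, section 1 says to read the SAP with the protocols, and the wording of 9.1 echoes the protocol's collection period. Protocol 15.3 can also be read as restricting SAEs to treatment-emergent ones, but it is ambiguous. This lowers the chance that the tables are built wrongly. It does not settle the matter, because the SAP writes TEAE elsewhere and leaves it out in these three places.

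Several limits on the consequence do stand:
- The serious and IMP-related overview rows are already treatment-emergent, and all AEs and SAEs are listed, so in a study of about 18 participants a pre-dose event could be traced.
- Analysis is descriptive, and no decision rule uses these tables.
- Protocol 14.2.4 requires a causality assessment for every AE, so a blank field should be rare.
- AESIs are not named in the endpoint and fall under it only as AEs. Some are defined against baseline or presuppose dosing, such as an ALT rise with an unexpected GCase fall or an unplanned increase in immunosuppression.

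A reader might go further and infer a definite inflation of event rates. With an assumed constant 0.1 to 0.5 events per person-year, full 16-week screening and 38-week follow-up, the proportion with an event would rise from 7.0-30.6% to 9.9-40.5%, a relative increase of 32-40%. The documents do not support this. They give no such rate, 16 weeks is a maximum, and equal rates before and after dosing are doubtful when vector and immunosuppressant effects are expected afterwards. With 104-week US follow-up the same assumptions give only about 8-14%.

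**Conclusion.** The mismatch is in the text and should be corrected. It is confined to the SOC/preferred-term tables in SAP 9.1.2, 9.1.5 and 9.1.7. Followed literally, these count pre-infusion events of participants who are later dosed, may disagree with the overview's TEAE rows, and can label a pre-infusion AE as FLT201-related when causality is blank.

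A reader might infer that the study's main safety result is contaminated. It is not: the primary endpoint is defined on TEAEs, and screen failures are outside the Safety Set.

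The effect on any one cohort is large only because cohorts are small: 33 to 50 points per event with 2 or 3 participants, and 100 with 1. The exposed share of the window is at most 30% with 38-week follow-up, 9.5% with 4 weeks of screening, and about 13% with Month 24 follow-up. The conclusion rests on a literal reading of the three subsections. It does not depend on how protocol 15.3 is parsed or on any assumed event rate.

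**What to change.** In SAP 9.1.2, 9.1.5 and 9.1.7, limit the summary tables to treatment-emergent events as defined in 9.1.1. That definition keeps events that begin before infusion and worsen during or after it. In the second paragraph of 9.1.3, change AEs to TEAEs; this is for consistency only, as the section already opens with TEAEs. Apply the rule that a missing relationship counts as related, for FLT201, only to treatment-emergent events. Present pre-infusion AEs, SAEs and AESIs in a separate listing so that nothing collected is lost.

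The cost is SAP wording and one listing. No new data are needed.
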